7.4 Visit 4/Day 15 (± 1)

It is estimated that this visit will take approximately 8 hours to complete.

- Interview
 - Update medications (those taken since the last visit);
 - Assess for AEs; and
 -
- Assessments
 - Assess application sites;
 - Perform abbreviated physical exam (only as applicable for evaluation of AEs);
 - Obtain weight;
 - Obtain and record vital signs;
 - Assess BSA for affected AD and record on body grid;
 - Photograph AD sites as applicable;
 -
 - Compliance check (weight check of study drug and review diary completion).
- Sample Collection
 - Collect a blood sample for PK prior to application at the study clinic and again at 1 hour (± 15 minutes), 4 hours (± 30 minutes) and 8 hours (± 1 hour) post application.
- Instructions
 - Dispense study drug;
 - Review dosing procedure and have the parent/guardian (caregiver)/subject apply the study drug to the affected areas; and

- Schedule Return visit for 1 week (Day 22) and remind parent/guardian (caregiver) and subject not to apply study drug in the morning before the visit and to bring all used and unused study drug to next visit.

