1 SCHEDULE OF ACTIVITIES

Week/Description	Screening	Week 0	Week 1	Week 2	Week 3	Week 4
Visit	V1	V2	V3	V4	V5	V6/ET
Study Day	-30 to -2	Day 1	Day 8 (±1)	Day 15 (±1)	Day 22 (±1)	Day 29 (±1)
Consent/Assent Refer to Section 6.1	X					
Inclusion/Exclusion Criteria Refer to Sections 5.1 and 5.2	X	X ^a				
Demographics Refer to Section 6.2	X					
Height/Weight/BMI and Body Surface Area (BSA) Calculation Refer to Sections 6.6 and 6.7	X	X ^{a,j}		X ^{a,j}		X ^j
Medical History (General, Surgical, Social and Medications) Refer to Sections 6.3.1 and 6.3.3	X	X				
Targeted Medical History – Atopic Dermatitis Refer to Section 6.3.2	X					
Physical Examination Refer to Section 6.4	X	X ^a	X ^c	X ^c	X ^c	X
Fitzpatrick Skin Type Assessment Refer to Section 6.5	X					
BSA% Involvement Refer to Section 6.8	X ^a	X ^a	X ^a	X ^a	X	
Corporate Confidential Information						
Photography (as applicable) Refer to Section 6.19	X ^a	X ^a	X ^a	X ^a	X ^a	X
Vital Signs Refer to Section 6.21	X	X ^a	X ^a	X ^a	X ^a	X

Week/Description	Screening	Week 0	Week 1	Week 2	Week 3	Week 4
Visit	V1	V2	V3	V4	V5	V6/ET
Study Day	-30 to -2	Day 1	Day 8 (±1)	Day 15 (±1)	Day 22 (±1)	Day 29 (±1)
12 Lead Electrocardiogram Refer to Section 6.22	X	X	X	X	X	X
Safety Laboratory Testing (Hematology, Chemistry and UA) Refer to Section 6.23.4.2	X	X ^k				X ^k
Pregnancy Testing – Females of Childbearing Potential only Refer to Section 6.23.4.1	X ^f	X ^{a,b}				X ^b
Pharmacokinetic Sampling Refer to Section 6.23.5		X ^g				X ^g
Corporate Confidential Information						
Registration Refer to Section 4.3		X ^a				
Dispensing Study Drug Refer to Section 8.3		X ^a	X	X	X	X
Training Subject/Parent/guardian (caregiver) (instructions) and Observation of Dose Application Refer to Section 8.4		X ^a	X	X	X	X
Dosing and Diary Completion Refer to Section 8.4		X-----X ^e				
Compliance Refer to Section 8.5		X ^a	X ^a	X ^a	X ^a	X
Concomitant Medications Refer to Section 6.24		X ^a	X ^a	X ^a	X ^a	X
Adverse Events and Serious Adverse Events Refer to Section 0	X	X	X	X	X	X
Application Site Assessments Refer to Section 6.18		X ^a	X ^a	X ^a	X ^a	X

- a Prior to dosing
- b For females of childbearing potential, urine pregnancy test will be done locally
- c Abbreviated examination of the skin and other areas with previous abnormal findings

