6 DESCRIPTION OF STUDY PROCEDURES

A description of study procedures listed in the Schedule of Activities is provided within the content of this protocol. Refer to the **Schedule of Activities 1** for additional information on the frequency of each procedure.

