6.4 Physical Examination

The physical examination will also include an examination of general appearance, skin, eyes, ears, nose, throat, neck/thyroid, lungs, heart, upper/lower extremities, lymph nodes, abdomen, musculoskeletal system and basic neurological assessment. Additional systems will be evaluated as needed. Physical exam findings must be recorded in the source documentation and include the date and name of the individual conducting the examination. Physical examinations must be performed by an individual licensed to conduct standard physical examinations.

Significant findings that are present prior to dosing with the study drug will be recorded in the eCRF as adverse events. Clinically significant findings present after dosing will be recorded as an adverse event in the eCRF.

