7 STUDY VISITS

The procedures and assessments to be performed at each visit are indicated in the Schedule of Activities. The timing of each visit (while on treatment) is relative to V2 when study registration occurs. An estimated time for the conduct of each visit is provided as a guide only to the study site personnel and study subject (parent/guardian/caregiver) for planning purposes. Note: it will not be considered a departure from the protocol if the visit length is shorter or longer than anticipated.

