10.2 General Guidelines

All observed or volunteered adverse events regardless of suspected causal relationship to the study drug are to be recorded on the appropriate eCRF from the time consent/assent is obtained through the end of the study as described in the following sections.

For all adverse events, the Investigator (Principal Investigator or Sub-Investigator) must pursue and obtain information adequate both to determine the outcome of the adverse event and to assess whether it meets the criteria for classification as a serious adverse event requiring immediate notification to the Sponsor or designee. For all adverse events, sufficient information should be obtained by the Investigator to determine the causality of the adverse event. The Investigator (Principal or physician Sub-Investigator) is required to assess causality. For adverse events with a causal relationship to the study drug, follow-up by the Investigator (Principal or physician Sub-Investigator) is required until the event or its sequelae resolve or stabilize at a level acceptable to the Investigator (Principal or physician Sub-Investigator) and Medical Monitor concurs with that assessment.

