11.5 Secondary Analysis

11.5.1 Safety

Safety evaluations will consist of adverse events (AEs), application site reactions, physical examinations, vital signs, ECGs, weight, and laboratory measurements (hematology, chemistry, and urinalysis). Full details will be specified in the SAP. A general description of the planned analysis is as follows:

- Descriptive statistics and frequency tables will be prepared as appropriate for physical examinations, vital signs, weight, ECG (HR, QTcF, PR, and QRS) and laboratory measurements (hematology, chemistry, and urinalysis).
- Adverse Events
 - AEs will be coded using the Medical Dictionary for Regulatory Activities (MedDRA); the version will be identified in the clinical study report.
 - AEs that occurred during the screening period will be listed separately and will not be included in the AE tabulations.
 - All other AEs that start on or after first dose will be considered TEAEs. Summaries will be presented by system organ class and preferred term, and further by severity and relationship to study drug. Application site AEs and any TEAEs reported by $\geq 5\%$ of subjects will also be tabulated.
 - The proportion of subjects who discontinue treatment due to an adverse event will be presented.
- Concomitant medications will be classified according to the World Health Organization (WHO) Drug Dictionary and will be presented in data listings.

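### The Schedule of Activities requires an abbreviated physical examination of every child at Days 8, 15 and 22, but the visit sections require it only when there is an adverse event to evaluate

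*Protocol*

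**What the plan says.** In the Schedule of Activities (Protocol section 1), the Physical Examination row is marked at all six visits. The entries for Visits 3, 4 and 5 carry footnote c: "Abbreviated examination of the skin and other areas with previous abnormal findings". Neither the row nor the footnote makes the examination depend on an AE. For what the examination consists of, the row says "Refer to Section 6.4".

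Sections 7.3 (Day 8), 7.4 (Day 15) and 7.5 (Day 22) list the same item in identical words: "Perform abbreviated physical exam (only as applicable for evaluation of AEs". Section 7.6 (Day 29 or early termination) lists a physical examination without a condition.

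Two sentences say which text to consult. Section 7 opens with "The procedures and assessments to be performed at each visit are indicated in the Schedule of Activities", and section 6 sends the reader to the Schedule "for additional information on the frequency of each procedure".

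Section 6.4 links the examination to safety reporting: "Clinically significant findings present after dosing will be recorded as an adverse event in the eCRF". Section 10.2 adds: "All observed or volunteered adverse events regardless of suspected causal relationship to the study drug are to be recorded". Incidence and severity of all AEs is a secondary endpoint (Protocol 3.3.2, SAP 6.3.2). For the examination data themselves, Protocol 11.5.1 states "Descriptive statistics and frequency tables will be prepared as appropriate for physical examinations", whereas SAP 7.9.9.4.3 plans a listing by subject only.

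**The concern.** Two instructions apply to the same procedure at the same three visits. If there is an AE to evaluate, they agree that an examination takes place. If there is none, the Schedule calls for an examination and the visit text lets the site leave it out.

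Under section 6.4 the examination is one route by which AEs come to light. An examination done only to evaluate an AE describes that event. It does little to find another that nobody has mentioned. Up to 12 sites in three countries take part, and SAP 7.5 pools their data. If some sites work from the Schedule and others from the visit text, AEs are ascertained in two ways within one single-arm summary, with no control group to absorb the difference. SAP 7.9.4 says protocol deviations will not be entered in the database, so a summary of deviations would not show which rule a site had followed.

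**Working it through.** The plan gives no figure to reproduce here. The check is a comparison of texts, followed by a count of what the conflict touches.

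**1. The two rules side by side (Visits 3, 4 and 5)**

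| Situation at the visit | Schedule, footnote c | Sections 7.3 to 7.5 |
|---|---|---|
| AE to evaluate | Examination | Examination |
| No AE to evaluate | Examination | None required |
| Scope | All skin, plus areas found abnormal before | Not defined beyond what the AE needs |

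The conflict is confined to the second row and occurs at all three visits.

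**2. How many examinations fall under both rules**

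Inputs: 32 subjects (Protocol 11.1), about 45 registered to give an estimated 32 completers (SAP 4.1), and post-baseline examinations at Visits 3, 4, 5 and 6 (Schedule).

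- 32 children: 3 × 32 = 96 of 4 × 32 = 128 child-visits.
- 45 children: 3 × 45 = 135 of 4 × 45 = 180 child-visits.

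These are the examinations governed by conflicting text. They are not counts of examinations that would be missed.

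**3. What could go unexamined**

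At all three visits the visit text lists, without condition, an AE interview, application-site assessment, vital signs and the body grid for affected skin. Set against footnote c, this leaves:

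- skin that was never treated and is not affected by atopic dermatitis;
- at Day 22, skin that was treated and has cleared, because after the Day 15 sampling drug goes only to involved areas (Protocol 4.1);
- non-skin areas that were abnormal before.

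A new finding in a previously normal area other than skin is outside footnote c, so neither rule looks for it.

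**4. What one child is worth in the summaries**

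Change in an incidence for one child = 100 / n percentage points.

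- n = 32: 100 / 32 = 3.1 points.
- n = 45: 100 / 45 = 2.2 points.
- Children aged 2 to 5, about 8 planned (SAP 4.1.2), for whom SAP 7.7 gives AEs separately: 100 / 8 = 12.5 points.

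For the table of events in at least 5% of subjects (SAP 7.9.9.2): 0.05 × 32 = 1.6, so 2 children are needed; 0.05 × 45 = 2.25, so 3 are needed. One missed child can therefore remove a term from that table. This shows how coarse the summaries are. It does not show that any child would be missed.

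**The case against.** The strongest reply is that the protocol already says which text to use. Sections 6 and 7 refer to the Schedule for what is done and how often, so a careful site would examine every child. That is a good reason to correct the visit text rather than the Schedule. It does not remove the conflict, because sections 7.3 to 7.5 are the lists that a site works through at the visit and they state a restriction explicitly.

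The reply is stronger on consequences, where a reader might infer more than the documents support.

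- **That AE incidence is understated.** This is possible but not shown. An event is lost only if nobody mentions it, the other checks do not reveal it, it lies within the scope of footnote c, and it has gone by the Day 29 examination. The documents give no rate for that combination.
- **That the AE must have been reported before the visit.** The AE interview belongs to the same visit and can trigger the examination. Section 10.2 also counts what staff observe, so a finding during the other checks can do so too.
- **That a child is not looked at between Day 1 and Day 29.** Treated skin, disease extent and vital signs are checked at each of the three visits. Finding enlarged disease also means looking beyond the treated area, although the purpose there is atopic dermatitis. Only the item called physical examination may be absent.
- **That findings anywhere outside the treated skin are at stake.** Footnote c does not reach previously normal areas other than skin. Where an earlier abnormality was significant, section 6.4 already makes it an AE, so the visit text also allows an examination for it.
- **That the number of omitted examinations can be estimated.** That would need a rate of visits with an AE and the share of sites following the visit text. The documents give neither.

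The direct effect on analysis is also small. The SAP only lists examination data, and the endpoint on clinically meaningful change covers laboratory values, ECG and vital signs, not the physical examination.

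**Conclusion.** The contradiction stands and appears in all three visit sections. It is an internal inconsistency of modest severity that bears on whether AEs are ascertained in the same way at every site.

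For a child with no AE identified at the visit, untreated or cleared skin and previously abnormal areas may not be formally examined between Day 1 and Day 29. It follows from the text alone that 96 of 128 planned post-baseline examinations (32 children) or 135 of 180 (45 children) fall under two rules. Any bias in AE incidence would be downward, since an omitted examination can lose an event but cannot add one. Its size cannot be computed from the documents, and the other checks at each visit and the Day 29 examination limit it. The conclusion assumes only that some sites might follow the visit text, which its explicit wording makes plausible.

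**What to change.** In sections 7.3, 7.4 and 7.5, delete the parenthesis after the abbreviated physical examination and put the content of footnote c in its place, so that the skin and any previously abnormal areas are examined in every child at each of these visits. One unconditional rule then applies at all sites, and the visit lists agree with the table to which sections 6 and 7 refer. This adds no procedure that the Schedule does not already contain.

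The edit is one phrase in three lists. The children are already in clinic for the application-site and body-surface-area assessments, so the cost is a few minutes per visit at sites that would have followed the visit text. The change would not extend the search to previously normal areas other than skin, and it should not be presented as doing so.

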7.5 Visit 5/Day 22 (±1)

It is estimated that this visit will take approximately 1.5 hours to complete.

- Interview
 - Update medications (those taken since the last visit);
 - Assess for AEs;
 -
- Assessments
 - Assess application sites;
 - Perform abbreviated physical exam (only as applicable for evaluation of AEs);
 - Obtain and record vital signs;
 - Assess BSA for affected AD and record on body grid;
 - Photograph AD sites as applicable;
 -
 - Compliance check (weight check of study drug and review diary completion).
- Instructions
 - Dispense study drug; and
 - Review dosing procedure and have the parent/guardian (caregiver)/subject apply the study drug to the affected areas.

Schedule Return visit for 1 week (Day 29) and remind parent/guardian (caregiver) that the last dose of study drug should be applied the night before the final visit (Day 28). They should also be reminded to bring all used and unused study drug and the scale, to final visit.

7.6 Visit 6/Day 29 (±1) or Early Termination (ET)

It is estimated that this visit will take approximately 1.5 hours to complete.

- Interview
 - Update medications (those taken since the last visit);
 -

- Assess for AEs.
- Assessments
 - Assess application sites;
 - Perform physical examination;
 - Obtain weight;
 - Obtain and record vital signs;
 - Perform a 12-Lead ECG;
 - Assess BSA for affected AD and record on body grid;
 - Photograph AD sites as applicable;
 - Corporate Confidential Information
 - Compliance check (weight check of study drug and review diary completion).
Collect all used and unused study drug and scale.
- Sample Collection
 - Collect blood samples for safety laboratory testing.
 - Collect urine sample for urine pregnancy testing (as applicable).

7.7 Unscheduled Visit(s)

An unscheduled visit will be scheduled every 7 to 14 days in order to follow-up on unresolved adverse events that were still present at the final visit (V6). Additionally, the Study subject may be asked to return for additional visits to follow clinically significant abnormal laboratory results.

7.8 Unscheduled Procedures

It may be necessary to collect unscheduled procedures as clinically indicated for evaluation of subject safety. Procedures completed at an unscheduled visit will be driven by the reason for the unscheduled visit. Should a skin irritation event occur, a patch testing can be performed, if feasible, to rule out an allergic/hypersensitivity event.

8 STUDY DOSING

8.1 Formulation, Packaging and Labelling

8.1.1 Formulation

MM36 1% is a white petrolatum based ointment. A list of all components in MM36 1%, is presented in Table 3. Each gram of MM36 1% w/w ointment contains 10 mg of active MM36.

Table 3 Components of MM36 1%

Components Ointment
MM36 1% w/w
Corporate Confidential Information

8.1.2 Packaging

Five labeled tubes will be assembled into a subject box. Each box will be labeled with a single panel label and tamper sealed. Five labeled subject boxes will be assembled into block kits. Each kit will be labeled with a 2-part tear away label and tamper sealed.

8.2 Storage

Study drug will be stored at the clinical site in a secured (limited access to authorized site personnel only) storage area. The investigational drug product will be stored at controlled room temperature (15°C to 25°C).

8.3 Dispensing

As reported in Nelson et al, 2006, “an average of 9.9 g/m² (equivalent of 1.0 mg/cm²) of a topical agent (by weight) are required by a disciplined operator to achieve a thin, even layer of ointment on a patient” (pp. 224). Therefore, to determine the number of grams (by weight) per day, the Investigator/designee will use the following formula:

Step 1 Formula to Calculate Grams (by weight) of MM36 1% to Use Per Dose:

$$\text{Overall BSA (m}^2\text{)} \times \text{Total (BSA \%)} \text{ of All areas of involvement that will be treated} \times 10 \text{ grams/m}^2 = \text{Grams of ointment per application}$$

Example: A six-year-old boy with 32% BSA involved areas of AD

$$0.7 \text{ m}^2 \times 32\% \text{ (or 0.32)} \times 10 \text{ grams/m}^2 = 2.24 \text{ grams/application}$$

Step 2 Formula to Calculate Grams Needed to Dose BID for 1 Week (7 Days):

$$\text{Grams of ointment needed per Application} \times \text{Number of applications Per day} = \text{Total grams of ointment needed per day} \times \text{Number of Treatment Days} = \text{Total Grams Needed}$$

Example continued:

$$2.24 \text{ grams} \times 2 = 4.48 \text{ grams} \times 7 = 31.36 \text{ grams}$$

Step 3 Formula to Calculate Number of MM36 Tubes of Study Drug (27 grams per each) Needed for 1 Week (7 Days) of Treatment:

$$\text{Total Grams Needed} \div 27 \text{ grams (weight per 1 tube of study drug)} = \text{Number of Tubes to be dispensed}$$

Example continued:

$$31.36 \text{ grams} \div 27 \text{ grams (weight per 1 tube of study drug)} = 1.16 \text{ tubes (dispense 2 tubes)}$$

The table below (Table 4) is provided as general guide to determine the amount of study drug to be dispensed based on a subject's BSA and their intended area of application. Exact calculation will be done on an individual basis. The Investigator or designee will enter the subject's overall BSA, BSA% involvement and intended number of treatments (until the next visit) into the dosing module in the eCRF. The number of tubes to be dispensed will be calculated.

Table 4 Estimated Dispensing Table

Age Range	Estimated ^a BSA m ² Of the Average 50 th Percentile for Males and Females	Approx ^b Grams of Ointment Needed for Application to Every 1% BSA Involvement	Grams (weight) of Ointment Required Per Application to a Minimum Involved Area of 25%	Grams of Ointment Required Per Application to a Minimum Involved Area of 35%
2 - 3	≥ 0.5 to < 0.7	0.07	1.75	2.45
4 - 6	≥ 0.7 to < 1.0	0.10	2.5	3.5
7 - 11	≥ 1.0 to < 1.3	0.13	3.25	4.55
12 - 13	≥ 1.3 to < 1.6	0.15	3.75	5.25
14 - 17	≥ 1.6 to < 1.9	0.20	5.0	7

^a Kuczmarski et al, 2000

^b Nelson, 2006

The subject/subject's parent/guardian (caregiver) will be provided a calibrated scale and measuring cups to dispense the calculated dose for each application. Procedure will be

discussed with the subject or parent/guardian (caregiver) at the site and documented that proper training occurred prior to first application (refer to [Appendix A](#)).

8.4 Dosing

The subject (parent/guardian (caregiver) will be instructed on proper application of the study drug and will apply the initial application on Day 1 at the study site. The proper dose dispensing procedure and use of the study drug will be demonstrated and observed by study staff to ensure subject (parent/guardian (caregiver) understand the instructions.

- For each dosing period, the subject, under the supervision of the parent/guardian (caregiver), or the parent/guardian (caregiver), will dispense the required amount of ointment (by weight) using the measuring cup(s) provided.
- The subject should wash his/her hands both before and after applying study ointment. If applied by the parent/guardian (caregiver), they should also wash hands before and after applying study ointment, but will also wear non-latex gloves (provided by the Sponsor).
- The subject (parent/guardian (caregiver) will apply a thin layer of ointment to affected areas twice daily (approximately 12 hours apart) for 28 consecutive days.
- It is recommended that the ointment be applied after showering/bathing. The skin should be dry prior to application. Important: Subjects should not swim or bathe or wipe application area for a minimum of 20 minutes after application of ointment.
- The ointment should be rubbed in gently and completely, avoiding contact with the eyes.
- Subject's (parent/guardian (caregiver) will be instructed not to administer the study drug in the morning on the day of the study visit to avoid any effect of the study drug on the assessments.
- An adult (≥ 18 years of age) parent/guardian (caregiver) will verify if the study drug was weighed appropriately and applied as directed. Application details will be recorded in the electronic diary.

